5.7 EFFICACY ASSESSMENTS

5.7.1 Sigmoidoscopy

Flexible sigmoidoscopy with biopsies will be performed at Screening (Visit 1) and Day 56 (Visit 7) or early discontinuation visit. At least 3 tissue samples are required from an area of active inflammation at Screening. On Day 56 (or early discontinuation visit), at least 3 tissue samples are required from the same region where Screening biopsies were obtained.

Additional biopsy samples may be collected at the Investigator's discretion for histological assessment.

The Endoscopic Finding Sub-score grading is provided in Appendix B. The UCEIS grading is provided in Appendix C. Each site will perform sigmoidoscopy at Screening (Visit 1) to evaluate eligibility (see Inclusion/Exclusion criteria). For efficacy evaluation, all endoscopic images (Visits 1 and 7 [or early discontuation visit]) will be reviewed centrally according to the procedure provided by the Institution conducting the central reading.

5.7.2 Mayo score

The Mayo Scoring System (Appendix B) for assessment of UC activity will be used for efficacy evaluation. The score will be determined at Screening (Visit 1) and Day 56 (Visit 7).

The Mayo Score is a discrete ordinal scale ranging from 0 (normal or inactive disease) to 12 (severe disease) and is a composite of 4 sub-scores: Stool Frequency Sub-score, Rectal Bleeding Sub-score, Endoscopic Finding Sub-score and Physician's Global Assessment Sub-score, each of which ranges from 0 (normal) to 3 (severe disease) [18]. The sub-scores are summed to give a total score that ranges from 0–12.

The partial Mayo Score is a 9-point scale that excludes the Endoscopic Finding Sub-score. It will be used for assessment of disease activity on Day 0 (Visit 2), Day 14 (Visit 3), Day 28 (Visit 4), Day 35 (Visit 5), Day 42 (Visit 6) and Day 90 (Visit 8).

5.8 PD ASSESSMENTS

5.8.1 Fecal calprotectin

Calprotectin is a cytosolic protein in neutrophilic granulocytes that correlates with neutrophilic infiltration of the intestinal mucosa [19, 20]. Fecal calprotectin is a marker of intestinal inflammation in UC. Fecal samples for analysis of calprotectin level will be collected at every study visit. On treatment days, samples will be collected pre-dose. Analysis will be conducted by a central laboratory.

5.8.2 Eosinophil count, serum eotaxin-1, hs-CRP and ECP

Blood samples for eosinophil countⁱ, eotaxin-1, hs-CRP and ECP^j will be collected at every study visit (excluding screening visit). On treatment days, samples will be collected pre-dose. Processing and storage of the samples are detailed in the Laboratory Manual. Analysis will be conducted by a central laboratory.

5.8.3 Eosinophil count and eotaxin-1 concentrations in biopsy tissue

Biopsy tissue samples for analysis of eotaxin-1 concentrations and eosinophil count will be collected at screening (Visit 1) and on Day 56 (Visit 7) or early discontinuation.

Analysis of eotaxin-1 and eosinophil count in biopsy tissue will be conducted by a central laboratory and the handling, storage, processing and analysis procedures will be described in the Laboratory Manual.

5.9 PK ASSESSMENTS

PK outcome is study drug (bertilimumab) concentration in the serum. PK parameters will include:

C_{max} Maximum bertilimumab serum concentration

 T_{max} Time to C_{max} (peak exposure)

C_{avg} Average bertilimumab serum concentration

C_{min} Minimum bertilimumab serum concentration

 λ_z Elimination rate constant

 $t_{1/2}$ Elimination half-life, calculated as $0.693/\lambda_z$.

Additional PK parameters may be calculated if deemed necessary.

PK blood samples will be collected at every study visit (excluding screening). On dosing days, blood samples will be collected pre-dose and at 30 (+15) minutes (immediately post-infusion) and 4 hours (±20 minutes) following the initiation of study drug administration. The actual sampling times will be recorded.

Processing and storage of the samples are detailed in the Laboratory Manual. PK analysis will be conducted by a central laboratory using a validated method.

6. INVESTIGATIONAL PRODUCT

6.1 IDENTITY OF INVESTIGATIONAL PRODUCT

Bertilimumab is a recombinant human IgG₄ monoclonal antibody that neutralizes human eotaxin-1 (eotaxin). The drug product consists of bertilimumab formulated in phosphate buffered saline (PBS) at pH 7.2 and at a concentration of 10 mg/mL, presented as a sterile, clear, colorless solution in 10 mL clear glass vials.

The formula for the PBS is sodium chloride 77 mM, monosodium phosphate 17 mM and disodium phosphate 50 mM.

Matched placebo glass vials will contain PBS.

Polysorbate 20, a non-ionic surfactant to prevent protein aggregation, is added to the bertilimumab or placebo formulationat the time of vialing or to the saline infusion bag prior to dosing. The Pharmacy Manual will indicate whether polysorbate 20 is to be added prior to dosing.

6.2 STUDY DRUG ADMINISTRATION AND DOSAGE

Bertilimumab (10 mg/kg) or placebo will be administered by intravenous infusion over 30 minutes. A pretreatment prophylactic regimen (as detailed in section 5.2) will be administered prior to dosing on each treatment dosing day (Days 0, 14 and 28) to reduce the likelihood of an infusion reaction.

6.3 Manufacturing of Study Medication

A cGMP vendor will perform the drug product and placebo manufacturing and release.

6.4 PACKAGING AND LABELLING OF STUDY MEDICATION

Bertilimumab vials or matching placebo will be packaged and labeled in compliance with GCP and local health authority guidelines. Each study center's hospital pharmacy facility will be responsible for handling and preparation of the study drug.

6.5 DISTRIBUTION AND SHIPMENT OF STUDY MEDICATION

Study drug will be packed and shipped in appropriate boxes. If, upon arrival at the clinical investigation site, the study drug appears to be damaged, the study monitor should be contacted immediately.

Each shipment of study drug supplies for the study will be accompanied by a shipment form describing the contents of the shipment, acknowledgement of receipt and other appropriate

documentation. The shipment form will assist in maintaining current and accurate inventory records. The study staff will confirm the receipt of clinical supply to the study monitor.

All study supplies should arrive at the Pharmacy/Investigational site in sufficient quantity and in time to enable dosing as scheduled. The Sponsor or its representative must notify the principal Investigator prior to dispatch of drug supplies with the anticipated date of their arrival.

6.6 STORAGE AND INSTRUCTIONS FOR PREPARATION AND INFUSION OF THE INVESTIGATIONAL PRODUCT

The study medication will be stored in each study center's hospital pharmacy facility. The study drug (bertilimumab or placebo) will be stored in glass vials under refrigeration at 2-8°C. The polysorbate 20, if not included during vialing and necessary for inclusion to the saline infusion bags prior to subject dosing, will be provided to the center's hospital pharmacy facility where it is to be stored, under frozen (-20°C) conditions.

Records should be kept by the pharmacist as to how much study drug was used by each subject. The study monitors must periodically check the study drug supplied to ensure expiry date and sufficient amount of study drug, and be sure that drug accountability is being performed at each visit, and the drug accountability logs (for study drug/placebo and polysorbate) are maintained.

All investigational products must be kept in a locked area with access to the study drug limited to designated study personnel.

Preparation of the study drug dose for administration must be carried out by a trained medical professional at the study center's hospital pharmacy using aseptic technique according to the Pharmacy Manual. The number of vials used as well as the study drug volume dispensed per dose will be recorded in the study logbook.

Only trained personnel under the supervision of either the Investigator or the local pharmacist are authorized to administer study drug to participating subjects.

6.7 ACCOUNTABILITY AND COMPLIANCE OF INVESTIGATIONAL PRODUCT

Each delivery must be acknowledged by the hospital pharmacist (or authorized study team member responsible for the investigational medicinal product) by filling in the receipt record form and returning it by fax to delegated CRO. Accurate, complete, and timely documentation for all distribution to the study staff and subjects will be maintained by the pharmacy and the study staff of the investigational site which may include confirmation of receipts of clinical supply, drug accountability logs, and other forms.

The hospital pharmacist (or authorized study team member responsible for the investigational medicinal product) is responsible for ensuring the supervision of the storage and allocation of these supplies, which will be forwarded to the Investigator at the appropriate time before administration. The Investigator may dispense investigational drug only to subjects enrolled in the study.

Drug accountability records must be maintained by the clinical investigation site at all times. At the last study visit, all used and unused investigational drug will be collected and drug accountability performed by the study staff. The study monitor will check these regularly during monitoring visits.

Unused drug supplies will be returned to the Sponsor. At the end of the study, all the clinical supply and the corresponding accountability forms must be returned to the Sponsor, the study

monitor or designee for reconciliation and destruction. A photocopy of these records must be kept at the clinical investigation site.

The inventory will be made available to the study monitor who will verify accountability and verify dose during the course of the study.

Study drug orders, records of study drug receipts, dispensing records, and inventory forms located at the site will be examined and reconciled by the study monitor periodically during and at the end of the study.

6.8 BLINDING AND RANDOMIZATION

Subjects will be block randomized centrally (i.e., not within each center), stratified by previous anti-TNF treatment to ensure that approximately equal proportions of subjects who received previous anti-TNF treatment will be in each of the two treatment arms.

A CRO will be responsible to assign and track the treatment randomization for each enrolled subject and to provide the randomization number to the sites. The randomization assignment for a subject will be made available to the pharmacist at the study site but not to any other person on the study staff nor to any of the Sponsor's personnel or blinded monitors.

However, if the identity of the test medication administered needs to be known in order to manage the subject's condition, the Principal Investigator may be allowed access to the database treatment emergency code for that subject and the test medication identified. All such occurrences should be documented in the study file. Treatment emergency codes should not be broken except in emergency situations and, if possible, the Sponsor should be contacted before the emergency code is accessed.

Whenever disclosure of the identity of the test medication is necessary, adequate procedures will be in place to ensure integrity of the data. Any unblinding will be documented in the study report with date, reason for identifying the drug and the name of all the person(s) who had to be unblinded.

6.9 CONCOMITANT THERAPY

At the screening visit, relevant treatments currently received by the subject will be recorded on the subject's CRF including treatment's name, indication, dose, total daily dose and start and stop dates. Any medications (including prescription, over-the-counter, herbal supplements and other health store-type products) to be taken during the study must be approved by the Investigator and recorded in the CRF.

6.9.1 Allowed Medications

The following concomitant medications/therapies will be allowed during the treatment period:

- Occasional use of NSAID and acetaminophen for headache, arthritis, myalgia, menstrual cramps etc., and daily use of low-dose (81-162 mg) aspirin for cardiovascular prophylaxis is permitted
- Mesalazine ≤ 4.8 g is allowed if the dose during the 2 weeks prior to the screening visit was stable; subject is to remain on stable dose through Visit 6 (Study Day 42).
- Systemic corticosteroids not exceeding the equivalent of 20 mg/day of prednisone (see Corticosteroid Comparison Chart below) are allowed if the dose during the 4 weeks prior to the screening visit was stable; subject is to remain on stable dose through Visit 6 (Study Day 42), excluding corticosteroid used in pretreatment prophylaxis.

• Cortiment (budesonide) up to a daily dose of 9 mg is allowed during the screening period and throughout the study owing to limited systemic absorption.

Table 1: Corticosteroid Comparison Chart

	Approximate Equivalent Dose, mg	Relative Potency
Hydrocortisone	20	1.0
Cortisone Acetate	25	8.0
Prednisone	5	4.0
Prednisolone	5	4.0
Methylprednisolone	4	5.0
Dexamethasone	0.75	30-150

Reference: Welsh GA, Manzullo EF and Nieman LK. The surgical patient taking glucocorticoids. 2007 UpToDate® www.uptodate.com.

Additional medications/therapies may be allowed at the discretion of the Investigator in consultation with the Sponsor. All concomitant medications used to treat AEs will be recorded in the subject's medical file and on the appropriate CRF page.

6.9.2 Prohibited Prior and Concomitant Medication

Medications having the potential to interfere with the study assessments are excluded throughout the trial and include:

- Use of vaccines or other immunostimulator within 4 weeks prior to screening or any time during the study.
- Use of >4.8 g mesalazine or equivalent within 2 weeks prior to the screening visit.
- Use of systemic corticosteroids exceeding the equivalent of 20 mg/day of prednisone within four weeks prior to the screening visit.
- Change in dose of immunosuppressive drugs (e.g., corticosteroids, 6-mercaptopurine [6-MP], azathioprine) within four weeks prior to the screening visit.
- Use of TNF-blockers (e.g., infliximab or adalimumab) within 60 days of the screening visit.
- Use of oral or parenteral antibiotics within two weeks prior to the screening visit.
- Use of chronic non-steroidal anti-inflammatory (NSAID) therapy.

In the interests of patient safety, and acceptable standards of medical care, the Investigator may prescribe treatment(s) at his/her discretion, which will be recorded on the subject's CRF.

7. SAFETY AND PHARMACOVIGILANCE

7.1 ADVERSE EVENT

An adverse event (AE) is any adverse change from the subject's baseline condition, whether or not considered investigational product related. This includes any subjective signs, symptoms or diagnosis, clinical significant deviation from baseline laboratory values or vital signs, or worsening (more severe, more frequent or increased in duration during the investigational product treatment) of the concomitant disease present at baseline visit (after initiation of investigational product treatment). Stable chronic conditions that are present prior to study entry and do not worsen during the study will not be considered AEs. Disease-related adverse events will not be considered AEs only if they worsen beyond what would be

expected in the normal progression of the disease. In all cases, the etiology should, as much as possible, be identified and the Sponsor notified.

An abnormal result of diagnostic procedures including abnormal laboratory or vital sign findings will be considered an AE if it:

- Results in subject's withdrawal by the Investigator
- Is associated with clinical signs or symptoms
- Is considered by the physician to be of clinical significance.

Adverse events reported by the subject or observed by the Investigator will be individually listed on an AE form in the CRF as follows: the specific event or condition, whether the event was present pre-study, the dates and times of occurrence, duration, severity, relationship to study medication, specific countermeasures and outcome.

The intensity or severity of the AE will be characterized as:

• Mild: Transient or mild discomfort; no limitation in activity; no medical

intervention/therapy required.

• Moderate: Mild to moderate limitation in activity - some assistance may be

needed; no or minimal medical intervention/therapy required.

• Severe: Marked limitation in activity, some assistance usually required;

medical intervention/therapy required; hospitalization possible.

The Investigator will document in his/her opinion the relationship of the AE to the investigational product (study medication) using the following criteria:

Category	Definition	
Unrelated	Clearly due only to extraneous causes, and does not meet criteria listed under possible or probable.	
Unlikely	Does not follow a reasonable temporal sequence from administration. May have been produced by the subject's clinical state or by environmental factors or other therapies administered.	
Possible	Follows a reasonable temporal sequence from administration, but may have been also produced by the subject's clinical state, environmental factors or other therapies administered.	
Probable	Clear-cut temporal association with administration with improvement on cessation of investigational medicinal product or reduction in dose. Reappears upon rechallenge. Follows a known pattern of response to the investigational medicinal product.	

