7.2 SERIOUS ADVERSE EVENT

A **serious** adverse event (SAE) is any adverse event occurring at any dose that suggest a significant hazard or side effect, regardless of the Investigator or Sponsor's opinion on the relationship to the investigational product and that results in, but may not be limited to, any of the following outcomes:

- death (regardless of the cause)
- a life-threatening adverse drug experience
- inpatient hospitalization or prolongation of existing hospitalization (any inpatient hospital admission that includes a minimum of an overnight stay in a health care facility)
- a persistent or significant disability/incapacity

a congenital anomaly or birth defect.

Important medical events that may not result in death, be life-threatening or require hospitalization may be **serious** when, based upon appropriate medical judgment, they may jeopardize the subject and may require medical or surgical intervention to prevent one of the outcomes listed above.

Hospitalization for elective treatment of a pre-study condition that did not worsen while on study and hospitalizations for treatment of non-adverse events (e.g., cosmetic surgery) are not considered serious adverse events.

Significant medical events are those, which may not be immediately life-threatening, but may jeopardize the subject and may require intervention to prevent one of the other serious outcomes listed above. Examples of such events are intensive treatment in an emergency room or at home for allergic bronchospasm; blood dyscrasias or convulsions that do not result in hospitalization; resulting in an adverse event will normally be considered serious by this criterion.

Inpatient hospitalization or prolongation of existing hospitalization means that hospital inpatient admission and/or prolongation of hospital stay were required for treatment of AE, or that they occurred as a consequence of the event. Hospitalization for elective treatment of a pre-study condition that did not worsen while on study and hospitalizations for treatment of non-adverse events (e.g., cosmetic surgery or diagnostic procedure) are not considered serious adverse events.

Any new SAE that occurs after the study period and is considered to be related (possibly/probably) to the investigational product or study participation should be recorded and reported immediately.

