8.3.7.1 Adverse Events

Adverse events will be coded to system organ class and preferred term using the latest version of Medical Dictionary for Regulatory Activities (MedDRA) and are graded by the Investigator in terms of severity and relation to study treatment. All data will be listed by subject. Only treatment emergent AEs (TEAEs) will be presented in summary tables.

TEAEs are the adverse events that occur during the observation period, and the pre-treatment adverse events or pre-existing medical conditions that worsen in intensity after start of study medication and within the observation period.

TEAEs will be summarized by treatment arm in terms of crude incidence rates. For each event the crude incidence rate is defined as the number of subjects experiencing the event divided by the number of subjects initially exposed to study drug, regardless of duration of exposure to study drug. In addition, for each event the worst severity grade and the "worst" Investigator's judgment on study drug relationship is considered for each subject and frequency tables by worst severity grade and by worst study drug relation are provided. In this analysis, a subject having experienced more than once events classified under the same preferred term (body system) will be counted only once in the number of subjects with that preferred term (body system).

Summaries of TEAEs will be presented by body system and by preferred term within each body system (MedDRATM Terminology). The percentage of subjects who experienced AEs coded with the same term will be tabulated by treatment group in descending order according to the incidence of AEs in the active treatment groups.

All reported adverse events will be listed independently of their onset date. Serious Adverse Events, causes of death and AEs leading to premature discontinuation of study drug will be summarized similarly and listed. Reasons for premature discontinuation of study drug will be listed and summarized by frequency tables on all analysis sets.

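### A sentence in Protocol 7.1 is inverted: it makes worsening beyond normal progression the ground for not counting a disease-related event as an AE, against the rest of 7.1 and the TEAE definition in 8.3.7.1

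*Protocol*

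**What the plan says.** Protocol 7.1 has one sentence aimed at events of the disease itself: "Disease-related adverse events will not be considered AEs only if they worsen beyond what would be", completed after a page break by "expected in the normal progression of the disease". The word *not* is in running text; it does not come from a gap or a redaction.

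The sentences around it read differently:

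- The section opens: "An adverse event (AE) is any adverse change from the subject's baseline condition, whether or not considered investigational product related".
- It goes on to include "worsening (more severe, more frequent or increased in duration during the investigational product treatment) of the concomitant disease present at baseline visit".
- The sentence just before the disputed one says: "Stable chronic conditions that are present prior to study entry and do not worsen during the study will not be considered AEs".
- The sentence just after it asks that, whatever the case, a cause be sought and the Sponsor told.

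Protocol 7.2 says that an SAE "is any adverse event occurring at any dose that suggest a significant hazard or side effect", with a listed serious outcome. It also says, twice, that admissions to treat something that is not an adverse event are not SAEs. Protocol 7.4 attaches the 24-hour reporting limit to SAEs. Protocol 8.3.7.1 includes among treatment-emergent events "pre-existing medical conditions that worsen in intensity after start of study medication". SAP 9.3 tabulates treatment-emergent AEs and SAEs, but the SAP gives no rule for disease-related events.

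**The concern.** Safety is part of the primary objective (Protocol 2.1), and bertilimumab had not been studied in ulcerative colitis before (Protocol 1.2.2). Worsening colitis is a foreseeable event in this population, and a safety table should show it. The disputed sentence is the only AE rule in the protocol specific to disease-related events, so a site deciding how to record a flare has good reason to consult it.

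Three outputs depend on the answer:

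- the treatment-emergent AE tables;
- expedited SAE reporting;
- the discontinuation data. Protocol 4.5 allows withdrawal for progression or relapse, and 5.4 requires that an AE, if among the reasons, be the one recorded. Whether a flare is an AE therefore changes the recorded reason for stopping and the 8.3.7.1 summary of AEs that led to stopping study drug.

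**Working it through.** The plan states no figure to reproduce. The check is a comparison of texts, plus one line of arithmetic for scale.

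**1. How each text classifies the same colitis event**

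| Text | Worsening within normal progression | Worsening beyond it |
|---|---|---|
| 7.1, opening definition | AE | AE |
| 7.1, clause on worsening of concomitant disease | AE, if the clause covers the study disease | AE, if the clause covers the study disease |
| 7.1, disputed sentence, plain reading | AE | not an AE |
| 7.1, disputed sentence, strict logic | AE | may be excluded |
| 8.3.7.1, treatment-emergent definition | TEAE | TEAE |

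In strict logic, *not … only if* makes excess worsening necessary for exclusion but not sufficient. The sentence then does not say that every such event is excluded. On either reading, though, the only disease events that can be excluded are those that exceed expectation, which is backwards.

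**2. From AE to SAE**

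- (a) Colitis worsens beyond normal progression and the patient is admitted.
- (b) A site applies the disputed sentence literally and records no AE.
- (c) Under 7.2 an SAE must be an adverse event, and admission for a non-adverse event is not an SAE.
- (d) The admission is not reported under 7.4.

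A site that starts from the opening definition records the same admission as an AE and reports it as an SAE.

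**3. Scale**

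Inputs: up to 42 subjects, randomised 2:1 (Protocol synopsis). Crude incidence is subjects with the event divided by subjects exposed (8.3.7.1).

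- Active arm: 42 × 2/3 = 28, and 1/28 = 3.6 percentage points per subject.
- Placebo arm: 42 × 1/3 = 14, and 1/14 = 7.1 percentage points per subject.

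If fewer than 42 are enrolled, each subject weighs more.

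**4. Does deleting *not* settle it?**

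Only in part. With the word removed, worsening beyond normal progression is treated as an AE, as the opening definition and 8.3.7.1 already do. Worsening within normal progression then ceases to be an AE under this sentence. It remains one under the opening definition and under 8.3.7.1, neither of which has an expectedness threshold. A second conflict is left.

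**The case against.** A reader might infer that colitis flares will simply disappear from the AE and SAE record. The documents do not support that, for four reasons.

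- The opening definition in 7.1 and the TEAE definition in 8.3.7.1 would both capture a flare, and many investigators would guess the intent of the faulty sentence.
- The next sentence in 7.1 asks for the Sponsor to be notified in all cases.
- Section 7.2 exempts admission for a pre-study condition only when it is elective and the condition has not worsened. This implies that admission for a worsened condition is not exempt. The other exemption is illustrated by cosmetic surgery and diagnostic procedures.
- Worsening also shows in other data: partial Mayo at every visit (Appendix A), calprotectin at every visit (5.8.1), and the listing of dropouts with reason, treatment and time (SAP 9.1).

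These points limit the consequence without removing the defect. Sponsor notification in 7.1 carries no deadline and requires no AE-form entry, so it does not stand in for 24-hour reporting. Efficacy scores and dropout listings do not feed the AE tables. The clause on concomitant disease may not cover the study disease, so it does not clearly override the one sentence that does. SAE reporting should not depend on investigators guessing what was meant.

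**Conclusion.** Wrong as written. The sentence in 7.1 reverses the rule that its own paragraph and 8.3.7.1 set out, and the SAP does not repair it. A flare beyond expected progression could go unrecorded as an AE, or unreported as an SAE, at sites that take the sentence literally. The likely result is the same event counted differently between sites, rather than uniform omission.

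Each subject reclassified moves an arm's rate by 3.6 points (active) or 7.1 points (placebo), assuming the full 42 are enrolled and treated. How many subjects would be affected cannot be stated, because the documents give neither a rate of worsening nor evidence of which sentence sites followed. The defect in the wording is certain; its effect on the data is possible but not shown.

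**What to change.** 1. Correct the sentence in Protocol 7.1 by removing the inverting *not*. State affirmatively that disease-related worsening beyond normal progression is an AE, and an SAE when a seriousness criterion in 7.2 is met.
2. Reconcile 7.1, 7.2 and 8.3.7.1 so that one stated rule covers disease-related events, including those within normal progression, where the three sections would otherwise still disagree. Say explicitly whether the study disease falls under the concomitant-disease clause.
3. Repeat that rule in SAP 9.3, so that the TEAE and SAE tables rest on it.
4. Notify sites of the correction.
5. Before database lock, query the data already collected for colitis worsening not entered as an AE or SAE: partial Mayo scores, concomitant medications, discontinuation reasons and hospitalisations.

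Cost: a short protocol clarification touching three sections, one paragraph in the SAP, a site letter and one round of data queries. No new assessment is needed, and no dose, schedule or treatment rule changes.
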